8.3 Subgroup Analysis

A pre-specified subgroup analyses will be performed for 1 stent versus 2 stent approach distal left-main PCI. For these subgroups, the primary endpoint and secondary endpoints will be evaluated. The subgroups will not have significant power, meaning the results are considered exploratory (hypothesis generating) only.

8.4 Description of Data

Patient demographics, medical history, risk factors, pre- and post-procedure lesion characteristics, procedure characteristics, and outcome variables will be summarized using descriptive statistics.

8.5 Calculating days to event

When calculating the days-to-event, the date the event took place will be compared to the date of informed consent, also in case a staged procedure took place. For stent thrombosis however, the date the event took place will be compared to the date of the index procedure, also in case a staged procedure took place.

In the EXCEL trial, where the OPC is derived from, the date of randomization was used as 'day 0'. By using the date of informed consent as 'day 0' for all components of the primary endpoint the POLBOS LM PoCE rate is comparable with the OPC.

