7.6 Staged procedures

Procedural "staging" in PCI subjects is defined as a planned elective second PCI procedure at a separate setting to optimally complete the PCI. The criteria for staging are left to the operator's best judgment. Given the complexity of the ULMCA patients it is anticipated that a substantial number of patients may fall into the category of staged procedures.

In general, the decision to stage is based on the overall extent and complexity of coronary disease, the case complexity (intra-procedure difficulty encountered by the operator), the duration of the procedure, assessment of radiation exposure, the total volume of contrast utilized, the clinical stability of the subject, and other subject-related factors (diabetes, renal function, etc.).

If the patient requires a staged procedure, this should be documented at the time of the index procedure and the reason(s) for staging must be documented in the eCRF and source documents. Furthermore, the need for staging, and all specific lesions planned to be treated during the staged procedure should be declared beforehand in the eCRF at the time of initial baseline procedure. Stented segment(s) treated during the initial baseline procedure should not be treated again during the staged procedure.

The recommended timing of a planned staged procedure is optimally within 4 weeks, but it is strongly recommended that it is completed within 45 days. A staged procedure will not affect the original follow-up schedule.

The residual SYNTAX Score is an objective measure of the degree and complexity of residual stenosis after PCI. A correlation has been found between residual SYNTAX Score post PCI and mortality³⁶. In the POLBOS study it is recommended to attempt achieving a residual SYNTAX Score ≤ 8 post PCI.

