Target vessel revascularization is any repeat percutaneous intervention of the target vessel or bypass surgery of the target vessel.

[Target Lesion Revascularization (TLR)]

Target lesion revascularization is defined as any repeat percutaneous intervention of the target lesion or bypass surgery of the target vessel.

[Clinically-Indicated Revascularization (CI-TLR/TVR)]

Revascularization will be considered ischemia-driven if the target lesion diameter stenosis is $\geq 50\%$ by QCA and any of the following criteria for ischemia are met:

- Positive functional ischemia study including positive FFR/iFR corresponding to the area served by the target lesion; or
- Ischemic ECG changes at rest in a distribution consistent with the target vessel; or
- Typical ischemic symptoms referable to the target lesion; or
- IVUS of the target lesion with a minimal lumen area (MLA) of $\leq 4\text{mm}^2$ for non left main lesions or $\leq 6\text{mm}^2$ for left main lesions. If the lesions are de novo (i.e. not restenotic), the plaque burden must also be $\geq 60\%$; or
- FFR of the target lesion ≤ 0.80 or iFR of the target lesion ≤ 0.89 .

A target lesion revascularization for a diameter stenosis less than 50% might also be considered ischemia-driven by the Clinical Events Committee if there was a markedly positive functional study or ECG changes corresponding to the area served by the target lesion.

STENT THROMBOSIS

(ARC)⁴²

Stent thrombosis should be reported as a cumulative value at the different time points and with the different separate time points. Time 0 is defined as the time point after the guiding catheter has been removed and the patient left the catheterization lab.

Timing:

- Acute stent thrombosis*: 0 - 24 hours post stent implantation
- Subacute stent thrombosis*: >24 hours - 30 days post stent implantation
- Late stent thrombosis†: 30 days - 1 year post stent implantation
- Very late stent/ thrombosis†: >1 year post stent implantation

* Acute/subacute can also be replaced by early stent thrombosis. Early stent thrombosis (0 - 30 days) - this definition is currently used in the community.

† Including “primary” as well as “secondary” late stent thrombosis; “secondary” late stent thrombosis is a stent thrombosis after a target segment revascularization.

Categories:

- Definite
- Probable
- Possible

Definitions of each category are as follows.

- **Definite stent thrombosis**

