Definite stent thrombosis is considered to have occurred by either angiographic or pathologic confirmation.

Angiographic confirmation of stent thrombosis*

The presence of a thrombus[†] that originates in the stent or in the segment 5 mm proximal or distal to the stent and presence of at least one of the following criteria within a 48-hour time window:

- Acute onset of ischemic symptoms at rest
- New ischemic ECG changes that suggest acute ischemia
- Typical elevation or depression in cardiac biomarkers (refer to definition of spontaneous MI)
- Nonocclusive thrombosis

- Thrombus Intracoronary thrombus is defined as a (spheric, ovoid, or irregular) noncalcified filling defect or lucency surrounded by contrast material (on 3 sides or within a coronary stenosis) seen in multiple projections, or persistence of contrast material within the lumen, or a visible embolization of intraluminal material downstream.
- Occlusive thrombus
 - TIMI 0 or TIMI 1 in-stent or proximal to a stent up to the most adjacent proximal side branch or main branch (if originates from the side branch).
- * The incidental angiographic documentation of stent occlusion in the absence of clinical signs or symptoms is not considered a confirmed stent thrombosis.
- † Intracoronary thrombus.

Pathological confirmation of stent thrombosis

Evidence of recent thrombus within the stent determined at autopsy or via examination of tissue retrieved following thrombectomy.

- **Probable stent thrombosis**

Either of the following occurred after stent implantation will be considered a probable stent thrombosis:

- Any unexplained death within the first 30 days[‡]
- Irrespective of the time after the index procedure, any MI* that is related to documented acute ischemia in the territory of the implanted stent without angiographic confirmation of stent thrombosis and in the absence of any other obvious cause

‡ For studies with ST-elevation MI population, one may consider the exclusion of unexplained death within 30 days as evidence of probable stent thrombosis.

- **Possible stent thrombosis**

Clinical definition of possible stent thrombosis is considered to have occurred with any unexplained death from 30 days following intracoronary stenting until end of trial follow up.

STROKE

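### Section 8.5 times stent thrombosis from the index procedure, while Appendix I classes it by time from stent implantation, so some early thromboses of staged stents would be tabulated as late

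*Combined protocol and SAP*

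**What the plan says.** Section 8.5 sets day 0 for time-to-event calculations. Most events are counted from informed consent. Stent thrombosis is the exception: "the date the event took place will be compared to the date of the index procedure, also in case a staged procedure took place".

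Appendix I (Stent Thrombosis) asks for reporting both cumulatively and by separate time points, and ties the classes to implantation:

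- acute: "0 - 24 hours post stent implantation"
- subacute: ">24 hours - 30 days post stent implantation"
- late: "30 days - 1 year post stent implantation"

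Its origin is given as follows: "Time 0 is defined as the time point after the guiding catheter has been removed and the patient left the catheterization lab". It does not say which procedure is meant when there is more than one.

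Appendix I also has a 30-day cut for deaths without an explanation. Probable stent thrombosis after implantation includes "Any unexplained death within the first 30 days". Possible stent thrombosis is "any unexplained death from 30 days following intracoronary stenting until end of trial follow up".

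Section 7.6 expects staging in a substantial number of patients and gives its recommended timing as "optimally within 4 weeks, but it is strongly recommended that it is completed within 45 days". Under Appendix I, a lesion treated at a staged procedure is a target lesion. Section 5.2 lists stent thrombosis as secondary endpoint 6 and does not restrict it to stents placed at the index procedure.

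**The concern.** For a stent placed at a staged procedure, the index date is not the implantation date. If the 8.5 clock sets the timing class, the thrombosis appears older than it is by the interval between the two procedures. The shift goes one way only: events in staged stents can move from acute or subacute towards late, never the reverse. Early stent thrombosis could therefore only be understated.

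Two groups could also apply different rules to the same event. Section 11.3 has the Clinical Event Committee categorise stent thrombosis by the protocol definitions, which means Appendix I, while the statistical analysis follows 8.5. An event adjudicated as subacute could be tabulated as late. What is at stake is the acute/subacute/late split and the 30-day figure for a secondary safety endpoint.

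**Working it through.** The plan gives no figure on this point to reproduce. The check is date arithmetic.

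**Inputs**

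- s = days from index to staged procedure. Section 7.6 gives 4 weeks (28 days) as optimal and 45 days as the strongly recommended limit. Days 7, 14 and 21 are illustrative.
- t = days from implantation of the staged stent to its thrombosis, in whole days from 0 to 30 (31 values).
- Cut-offs from Appendix I: 24 hours (taken as day 1) and 30 days. The subacute and late windows both name day 30; here it is counted as subacute.

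**Rule**

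The Appendix I class uses t. The 8.5 clock uses s + t. An event that is early under Appendix I (t ≤ 30) becomes late under 8.5 when s + t > 30, that is, when t ≥ 31 − s. The number of whole-day lags affected is s when s ≤ 30, and all 31 when s > 30.

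| Staging day s | Lags t relabelled late | Count of 31 | Acute event (t = 0 or 1) becomes |
|---|---|---|---|
| 0 (index stent) | none | 0 | unchanged |
| 7 | 24 to 30 | 7 | subacute |
| 14 | 17 to 30 | 14 | subacute |
| 21 | 10 to 30 | 21 | subacute |
| 28 | 3 to 30 | 28 | subacute |
| 31 or later (e.g. 45) | 0 to 30 | 31 | late |

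Example for s = 14: a thrombosis at t = 16 gives 14 + 16 = 30, still early. At t = 17 it gives 31, now late.

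With t measured from implantation of the affected stent, every event at t = 0 to 30 stays early whatever the staging day.

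**Probable versus possible**

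Definite stent thrombosis rests on angiographic or pathological confirmation and has no 30-day cut. The myocardial infarction route to probable applies at any time. Only an unexplained death can move, from probable to possible, and only if its 30-day count is taken from the index date. The condition is again s + t > 30.

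**The case against.** The best defence is that the two sections do different jobs. Section 8.5 supplies a time variable for the Kaplan-Meier summaries in 8.5.3 and mentions neither the timing classes nor the definite/probable/possible categories. Classification belongs to the Clinical Event Committee under Appendix I. A single per-patient origin is a reasonable choice for a cumulative curve. This reading is possible, but 8.5 does not limit itself to curves, and Appendix I wants results by separate time points as well as cumulatively. A programmer following 8.5 literally would use the index date for both. The comparability argument in 8.5 does not help either: it defends consent as day 0 for the components of the primary endpoint, and stent thrombosis is not one of them.

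The defence is right about reach. Segments stented at the index procedure should not be treated again at staging (Section 7.6), and lesions other than the left main bifurcation receive XIENCE stents (Sections 4 and 7.4). The issue therefore falls mostly on staged stents outside the left main bifurcation. The two BiOSS LIM registries in Section 2.2.1 (60 and 74 patients) reported no in-stent thrombosis and no definite stent thrombosis respectively, so few events may arise.

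Three stronger inferences are tempting, and the documents do not support them:

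- **That 8.5 turns every early thrombosis of a staged stent into a late one.** This is true only for staging after day 30. With earlier staging, the shorter lags stay early.
- **That 14/30 = 47% (day 14) and 28/30 = 93% (day 28) are misclassification rates.** They are shares of calendar time. Reading them as shares of events needs a constant hazard over 30 days, which the documents do not give.
- **That 8.5 lowers the definite/probable count.** The committee applies Appendix I, and nothing in 8.5 redirects the cut for unexplained deaths to the index date.

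**Conclusion.** The inconsistency is real and should be reconciled before analysis. For stents placed at a staged procedure, 8.5 and Appendix I give different clocks, and no section says which sets the timing class or the 30-day figure. Applied as written, 8.5 would label as late those thromboses of staged stents with s + t > 30: only the longer lags when staging is early, nearly all at four weeks, and all after day 30.

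The consequence is limited. Stent thrombosis is a secondary endpoint outside the primary composite, so the primary analysis and the sample size do not change. Stents placed at the index procedure are timed correctly, and the total by 12 months is nearly unchanged. Any effect on probable versus possible is conditional on the 8.5 clock also being used for unexplained deaths. The documents give neither the number of staged patients nor an expected number of thromboses, so the number of events misclassified cannot be calculated.

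**What to change.** Amend 8.5 to state three things:

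1. The stent thrombosis timing class and early (30-day) reporting run from implantation of the affected stent, whether placed at the index or a staged procedure, consistent with Appendix I.
2. The index date serves only as the per-patient origin for cumulative Kaplan-Meier curves.
3. The 30-day cut for unexplained deaths follows Appendix I, with the plan naming which planned implantation (index or staged) starts the count. Appendix I does not settle this for a patient with two implantation dates, so the sponsor needs to choose and write it down.

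The cost is about a sentence of text and use of the staged procedure date. The documents do not list that date as a data item. It should be obtainable, because staging is documented in the eCRF (Section 7.6) and films of staged procedures are collected (Section 14.5). No new patient assessment is needed.

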8.5.1 Continuous variables

For all continuous variables the number of observations, mean, standard deviation and the 95% two-sided confidence interval for the mean is calculated. When required also median, Q1 and Q3 will be presented.

8.5.2 Categorical variables

Categorical variables are summarized by treatment in frequencies, percentages, a 95% two-sided confidence interval for the percentage is calculated.

8.5.3 Time dependent variables

Time dependent variables will be summarized by frequency and by Kaplan-Meier estimates and its 95% confidence intervals.

8.6 Missing data

Every effort will be undertaken to minimize missing data. Kaplan-Meier estimates will censor incomplete data at the date of last available follow-up information, assuming complete reporting of all events up to that date and event status unknown after that date.

Other missing information will be assumed Missing Completely at Random (MCAR). No imputation will take place for these data, nor is any sensitivity analysis planned.

9 SAFETY REPORTING

9.1 Serious Adverse Events (SAEs) Definitions

An AE is defined as any untoward medical occurrence, unintended disease or injury, or untoward clinical signs (including abnormal laboratory findings) in patients, users or other persons, whether or not related to the investigational medical device.

An AE is classified as “serious” if the event:

- Led to death;
Note: death is an outcome, and the term ‘death’ should not ordinarily be reported as the SAE. The immediate cause of death should be specified (eg, ‘cardiorespiratory arrest’), unless the cause of death is not known or cannot reasonably be discerned.
- Led to serious deterioration in the health of a patient that:
 - Resulted in a life threatening illness or injury;
Note: life-threatening means that in the opinion of the investigator, the subject was at immediate risk of death from the event as it occurred. This does not include an event that, had it occurred in a more severe form, might have caused death.
 - Resulted in a permanent impairment of a body structure or a body function;
 - Required in patients hospitalization or prolongation of existing hospitalization;
Note: hospitalization is defined as inpatient admission, overnight. Hospitalization does not include presentation and care within an emergency department.
 - Resulted in medical or surgical intervention to prevent permanent impairment to a body structure or a body function.
- Led to fetal distress, fetal death or a congenital abnormality or birth defect.

NOTE: Planned hospitalization for a pre-existing condition, or a procedure required by the protocol, without unusual deterioration in health, is not considered an adverse event.

9.2 Anticipated Adverse Device Effects

Anticipated adverse device effects for the BiOSS LIM C (and ALEX Plus) stent are described in the protocol (section 9.5). For safety reporting purposes, the list of known risks in section 9.5 will serve as Reference Safety Information. If the applicable device Instructions For Use’s (IFUs) are updated during the study with a significant impact, section 9.5 may be amended.

9.3 Device Malfunctions

If the investigator observes device malfunctions that led or might have led to a death or serious deterioration in health of a patient, user or other person, or has complaints with regard to defects in the medical devices, the investigator shall, within 24 hours of such observation, report such device malfunction or complaint to the device manufacturer, with a copy of the report to the sponsor. Sponsor shall be responsible to take necessary actions in response to a device malfunction to protect the safety of the trial patients, e.g. temporary suspension of the trial. The device manufacturer shall be responsible for handling all complaints and reported device malfunctions in respect of the quality of medical devices, for determining the measures to be taken due to such observations or complaints and for ensuring that all necessary actions are taken including, but not limited to, any necessary action in connection with the recall of the medical devices or the reporting of incidents to competent authorities if deemed appropriate by the device manufacturer. Discussions regarding such device malfunction or complaints will be held between the device manufacturer and the participating site.

9.4 SAE Reporting

The investigator will monitor the occurrence of Serious Adverse Events (SAEs) for each patient during the course of the study. For the purpose of this protocol, the reporting of SAEs begins directly after patient has signed informed consent through the last follow-up visit. If an event fulfills the criteria for SAE, then this shall be reported in the eCRF immediately, but at the latest within 24 hours of the clinic study staff having become aware of this, including their judgment regarding causal relationship of the event to the trial. At the time the event is reported in the eCRF, no event-supporting source documentation needs to be sent. Event supporting source documents will be requested by the sponsor (via monitoring organization and/or CRO) for the purpose of potential clinical event adjudication and reporting purposes. All SAEs will be followed until the event has been resolved (with or without sequelae).

Sponsor is responsible for the classification of serious adverse events and ongoing safety evaluation of the clinical investigation and shall review the investigator's assessment of all serious adverse events and determine and document in writing the sponsor's determination of seriousness and relationship to the investigational device; in case of disagreement between the sponsor and the principal investigator(s), both opinions shall be reflected.

Safety reporting will be in accordance with "Clinical investigation of medical devices for human patients (ISO 14155:2011, IDT) and the "guidelines on medical devices vigilance system" by the

European Commission (MEDDEV2.12 rev 08, Jan 2013) and in compliance with local country law. Primary endpoints will be collected as SAEs and presented in periodic reports, however will be excluded from expedited reporting. These include the following events:

- all-cause mortality
- Stroke (modified Rankin Scale (mRS≥1)
- Any Myocardial Infarction (includes non-target vessel territory)
- Any unplanned revascularization for ischemia (includes all target and non-target vessels)

9.5 Risk Analysis

Percutaneous coronary interventions (PCI) and intravascular stenting may offer certain advantages as compared to conventional surgical techniques. In addition, coronary stenting with DES have been performed successfully for several decades and is considered a standard treatment for coronary revascularizations. Thus, there is extensive clinical and commercial experience worldwide with cardiac catheterization and interventional procedures and it is expected that the procedural risks in this study and existing stenting procedure will not be significantly different. Aside from the potential direct benefits of a *dedicated* bifurcation stent to the patient included in this study, there may be benefits to future patients based upon the results of the study.

With any procedure there are risks and complications. The following is a list of known adverse events (alphabetical order) that may result from stent intervention. This list serves as Safety Reference Information for this study and presents all adverse events that will be considered anticipated.

- Allergic reactions
- Aneurysm
- Arrhythmias
- Arterial wall dissection
- Bypass rupture
- Cardiac tamponade
- Death
- Fever
- Fistula formation
- Haemorrhage
- Hypotension/Hypertension
- Infection and pain in vascular access site
- Myocardial infarction

- Prolonged angina pectoris
- Pseudoaneurysm
- Reactions for antiplatelet (antithrombotic) and contrast preparations
- Renal failure
- Repeated vessel narrowing
- Stroke
- The need for urgent CABG (Coronary Artery Bypass Graft) procedure
- Thrombosis (acute, subacute and chronic), embolism
- Unsuccessful placing of the stent in the planned area
- Vascular spasm
- Vessel closure
- Vessel perforation

